Within this study, HFASD participants assigned to the experimental group will wear the silver plated stainless steel *ProFoveate™* pellets strategically placed on their ears and held in place by the adhesive tape continuously for four weeks.

Study Treatment Instructions

Parents of children assigned to the experimental group will be given instructions on how to use the *ProFoveate™* pellets. The follow instructions will be included on a brochure (See supporting materials) and given to parents of children in the experimental group during visit 2:

TITLE: The Effects of *ProFoveate™* on Reducing Self- Stimulating Behaviors In Children Diagnosed With Autism Spectrum Disorders.

PI: [name]

Co-I: [name]

- 1) The *ProFoveate™* pellets are to be placed on the occiput of the right ear as indicated in the picture below.
- 2) Generally, the *ProFoveate™* pellets should be changed every 2 to 3 days or when they fall off.
- 3) Before applying, the skin should be thoroughly cleaned with alcohol and the tape applied with a good seal.
- 4) Check regularly to ensure that the pellets are in place.
- 5) Write down the date on the *Patient Diary Sheet* each time the pellets are checked.
- 6) You will be supplied with a packet of 50 pellets to use as needed during the 28 days of *ProFoveate™* intervention. All unused pellet are to be returned during the last visit.

Parents and children will be shown exactly where to place the pellets on the ear. Specifically, the Occiput point will be identified for each participant. In traditional Chinese medicine, the Occiput point on the ear may be used to influence brain and spinal cord function. Note in particular the proximity of the vestibular nerve (yellow) to the skin anterior to the ear canal and medial to the pinna on the ear in Figure 2 below. The Occiput point we want to use is behind the ear and lateral to a projection of the vestibular nerve (Figure 3).

[figure not shown]

Figure 2. http://images.emedicinehealth.com/images/eMedicineHealth/illustrations/ear_cutaway.jpg

[figure not shown]

Figure 3: Occiput point on ear.

Study Treatment Compliance

Parents will be provided with a Patient Diary Sheet (see supporting documents) and will be instructed to perform and document daily checks for placement of the pellets.

TITLE: The Effects of *ProFoveate*™ on Reducing Self- Stimulating Behaviors In Children Diagnosed With Autism Spectrum Disorders.
PI: [name]
Co-I: [name]

Device Dispensing and Disposition

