
Parents of each participant in the experimental group will be given a one month supply of silver plated stainless steel pellets (50 pellets) following group assignment at the initial study visit. Used pellets (those removed each time the pellets are changed) will be discarded. Unused pellets will be returned at the final study visit.

Study Design and Procedures

Schedule of Time and Events

Study Procedures	Visit 1	Visit 2	Study Intervention (or no-treatment control) Period	Visit 3	Visit 4
	Day 1	Day 2	Days 2-29	Day 30-34	Day 30-34
Informed Consent	x				
Hearing Screening	x				
TONI-4	x				
Randomization	x				
SSIS – Student Form	x			x	
TOPL-2	x			x	
Parent Questionnaire	x			x	
SSIS – Parent Form	x			x	
Video Taping	x			x	
EEG		x			x
Dispense Test Article ^a		x			
Log in returned Test Article ^a					x
Study Treatment ^a		x	x		
Treatment Compliance ^a		x	x		
Adverse Event Review		x			x

EEG = electroencephalography; TONI-4 = Test of Nonverbal Intelligence 4; SSIS = Social Skills Improvement System; TOPL-2 = Test of Pragmatic Language -2

^aOnly for those subjects assigned to the experimental group

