This is a pilot study aimed at examining the effects of *ProFoveate*™ intervention on reducing some of the hallmark characteristics of HFASD. Specifically, we are interested in documenting any changes in self-stimulating behaviors or social skills and neural activity as reported by parents and EEGs. A two group control group design will be utilized where both the experimental group and control group of individuals with HFASD will receive assessments of self- stimulating behaviors, social skills and neural activity at baseline. The experimental group will receive the *ProFoveate*™ intervention followed by reassessment of both the experimental and control groups at the end of the study. The target participants are 30 children diagnosed with HFASD between the ages of 10 and 17 years and their parents. This older age group was chosen because the participants must able to apply and monitor the *ProFoveate*™ pellets. Participants will be recruited by sending out flyers (See Flyer attachment) to autism support groups and to previous clients of a social skills program at the UALR Speech and Hearing Clinic. Participants who are interested in participating will make an appointment. At that time the consent form will be reviewed and any questions will be answered by the principal investigator. Participants will be given as much time as needed to review the consent/assent forms (See consent and assent form attachments). Those who provide consent/assent and have a documented diagnosis of ASD (autism, Asperger's syndrome, or PDD-NOS) will be assessed. Participants will come to the UALR Speech and Hearing Clinic for four visits. Visit

TITLE: The Effects of *ProFoveate*™ on Reducing Self- Stimulating Behaviors In Children Diagnosed With Autism Spectrum Disorders.

PI: [name]

Co-I: [name]

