
pressing task that provides the accuracy of their responses and reaction time. Following EEG recordings, ERP analysis time windows will be set *post hoc* permitting a -100 ms pre-stimulus baseline and a post-stimulus time that extends well beyond the P300 latency (e.g., epoch of -100 to 700 ms). EEGs will undergo ocular artifact rejection and be baseline corrected prior to production of an average to all target stimuli. P300 amplitude and latency measures will also be taken. These procedures are expected to last no more than one to one and a half hours in a single session or a split session depending on the needs of the participant. During the administration of ERP procedure, the PI will not be aware if the child participant undergoing the procedure is in the control group or experimental group. This approach will support internal validity and minimize the potential for investigator bias. Sample waveforms showing several ERP components, including [P300](#) are presented in Figures 4.

[figure not shown]

Figure 4: <http://en.wikipedia.org/wiki/File:ComponentsofERP.svg>

Following initial assessment, child participants will be randomly assigned to either the control group (15 participants) or the experimental group (15 participants). Participants in the experimental group will be required to wear the *ProFoveate*™ metal pellets held in place by small adhesive bandages strategically placed on their ears during days 2-29. Participants in the experimental will be told to return for the final assessment on days 30-34 following cessation of treatment. Participants in the control group will receive no study intervention. Participants in the control group will be told to return for final assessment on days 30-34 following initial assessment.

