Risks include the fact that the adhesives used to hold on the pellets contain trace amounts of latex. If the pellet causes the development of an abrasion, the skin should be allowed to rest 24 hours after which the pellet should be positioned at alternate positions such as shen men or point zero or P6 WRIST position. If the pellets are ingested, drink plenty of fluids and the pellets will be expelled from the body naturally.

Risks Associated with ERP Recordings

Risks associated with ERP recordings are minimal and pose no greater risk to individuals than would occur in daily life. All electronic instrumentation is appropriately grounded, all auditory stimuli are calibrated to safe auditory presentation levels, and all metal surface electrodes are cold sterilized. In the PI's clinical experience, only 1 patient in the 6 years the lab has been in existence experienced a small rash related to a reaction from the medical grade tape we use to secure the electrodes to the face. No other adverse reactions have been reported to any other products we use to prepare the skin surface for the electrodes, and the securing of electrodes to the head. Having to wear electrodes with wires hanging off the head may be disconcerting to some, but we have never experienced early termination of an ERP test because of electrode-related discomfort. Finally, having to sit and actively attend to the visual or auditory stimuli may be uncomfortable to some, but we have never experienced early termination of an ERP test because of discomfort related to our standard procedures.

Other Study Risks

It is possible that a breach of subjects' confidential information could occur. Measures will be implemented to minimize this risk as described in the Data Handling and Recordkeeping section below.

Potential Benefits

The potential benefits to science and humanity that may result from this study include the possibility of finding a treatment procedure for reducing self-stimulating behaviors in children with ASD. This study will provide information to researchers and professionals working with children diagnosed with high functioning autism to help them manage self-stimulating behaviors in this population.

Safety Assessments

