Eliciting and Reporting Adverse Events: Subjects will be assessed for the occurrence of adverse events at each study visit. All adverse events occurring during the course of the study will be recorded on the Adverse Event Case Report Form and reported in accordance with the applicable regulations.

Identification of Adverse Events: An adverse event is defined as any new medical problem, or exacerbation of an existing problem, experienced by a subject while enrolled in the study, whether or not it is considered device-related by the investigator.

Relationship of Adverse Events to the investigational Device: The study physician will assess the relationship of the adverse event to the investigational device. The relationship will be assessed using the following categories:

- **Definitely Related:** A direct cause and effect relationship between the investigational device and the adverse event exists.
- **Possibly Related:** A direct cause and effect relationship between the investigational device and the adverse event has not been clearly demonstrated, but is likely or very likely.

TITLE: The Effects of *ProFoveate*™ on Reducing Self- Stimulating Behaviors In Children Diagnosed With Autism Spectrum Disorders.

PI: [name]

Co-I: [name]

- Unlikely Related: A direct cause and effect relationship between the investigational device and the adverse event is improbable, but not impossible.
- Unrelated: The adverse event is definitely not associated with the investigational device.

Serious Adverse Events: Each adverse event will be assessed for its seriousness using the criteria outlined below. The term serious adverse event is not synonymous with a “severe” adverse event, which may be used to describe the intensity of an event experience by the subject. An adverse event will be classified as serious if it meets any of the following criteria:

- Results in, or contributes to, a death;
- Life-threatening (i.e., the subject was, in the opinion of the investigator, at risk of death at the time of the event, but it does not include an event that, had it occurred in a more severe form, might have caused death);
- Results in permanent disability or incapacity (i.e., permanent impairment of a body function or permanent damage to a body structure);
- Requires in-patient hospitalization or prolongs hospitalization;
- Necessitates medical or surgical intervention to preclude a permanent disability or incapacity;

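### No scheduled adverse event review falls on Days 3-29 of the 28-day wear period, and the text and the schedule disagree on which visits carry a review

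*Protocol*

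**What the plan says.** Four parts of the protocol bear on this.

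- **Elicitation.** Safety Assessments (Eliciting and Reporting Adverse Events) says: "Subjects will be assessed for the occurrence of adverse events at each study visit". It also requires every event during the study to be entered on the Adverse Event Case Report Form. It describes no telephone call, interim contact or diary item for adverse events.
- **Schedule.** Under Study Design and Procedures, "Participants will come to the UALR Speech and Hearing Clinic for four visits". The Schedule of Time and Events puts these on Day 1, Day 2 and, for both Visits 3 and 4, Days 30-34. Its row "Adverse Event Review" is marked at Visits 2 and 4 only. Visit 1, the intervention column and Visit 3 are blank.
- **Exposure.** The pellets are held by "small adhesive bandages strategically placed on their ears during days 2-29". The Study Treatment Instructions supply a packet "to use as needed during the 28 days of *ProFoveate™* intervention".
- **Foreseen harm and daily record.** The section on device risks says: "If the pellet causes the development of an abrasion, the skin should be allowed to rest 24 hours", followed by a change of position. Under Study Treatment Compliance, parents "will be instructed to perform and document daily checks for placement of the pellets" on a Patient Diary Sheet. The Study Treatment Instructions mention writing down the date of each check. The diary applies to the experimental group only.

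**The concern.** The protocol promises complete recording of adverse events but arranges to ask about them only before and after nearly all of the exposure. The harm it foresees is local and can be brief. Its own Mild grade is discomfort that does not disrupt daily activity, and events of that kind are the easiest to forget or misdate over several weeks.

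Dates matter for two reasons. The study physician must judge whether each event is related to the device. Electrodes are also taped to both mastoids at the EEG visits, close to the patch site behind the ear, so an undated skin reaction there is harder to attribute to one or the other. In addition, an abrasion that leads to a rest and a new position changes exposure, and the diary as described has no place to note this.

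The protocol calls this a pilot and says that use of the product in autism has not been explored before. Local tolerability over four weeks is something that such a pilot can usefully describe.

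**Working it through.** **Inputs**

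- Wear period: Days 2-29 (Schedule of Time and Events; Study Design and Procedures).
- Visit days: 1, 2, 30-34 and 30-34 (Schedule of Time and Events).
- Visits with a review: all four (Safety Assessments) or Visits 2 and 4 only (Schedule of Time and Events).

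**Step 1. Reproduce the stated wear length.** 29 − 2 + 1 = 28 days, which agrees with the 28 days in the Study Treatment Instructions.

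**Step 2. Count wear days with no visit.** No visit falls on Days 3-29. That is 29 − 3 + 1 = 27 of the 28 wear days. The remaining one, Day 2, is the day on which the schedule has the pellets dispensed.

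**Step 3. Gap between reviews.** From Visit 2 to a final review on Day 30: 30 − 2 = 28 days. To a final review on Day 34: 34 − 2 = 32 days.

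**Step 4. Recall by day of event.** Recall = day of final review − day of event.

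| Event on | Final review Day 30 | Final review Day 34 |
|---|---|---|
| Day 2 | 28 days | 32 days |
| Day 15 | 15 days | 19 days |
| Day 29 | 1 day | 5 days |

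**Step 5. Does the disagreement over visits change this?** No. Reading the text literally adds reviews at Visit 1 (Day 1, before wear under the schedule) and Visit 3 (Days 30-34, after wear). Neither falls on Days 3-29, and Visit 3 shares its window with Visit 4, so the range of 28 to 32 days stands on both readings.

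**Step 6. Effect of a daily entry.** Recall in the experimental group would fall to about one day. Controls have no diary, so their gap between reviews would stay at 28 to 32 days.

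**The case against.** The case on the other side is that asking at visits is a workable choice for a pilot with 30 children, four visits and an adhesive patch. It also rests on the following points, most of which stand as limits on the claim.

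- **Capture is wider than elicitation.** A reader might infer that events can be captured only at visits. The protocol does not say so. The duty to record covers all events, and the reporting clocks for deaths and unanticipated device effects run from learning of the event. Spontaneous reports are not barred.
- **The diary sheet was not seen.** A reader might infer that it holds nothing except dates. The instructions mention only the date, but they do not exclude a comment or skin field. The brochure and consent form were not available either, and could carry an instruction to call.
- **Abrasions.** A reader might infer that families manage abrasions at home and that these will usually have healed before anyone asks. The risk section names neither family nor home, and the protocol gives no healing time. A rest and a new position might also make the event memorable.
- **Use of the result.** A reader might infer that a clean safety record would be an artefact, or that it is certain to be carried into later studies. The first cannot be shown from the protocol. On the second, the protocol says only that further studies may follow. It lists no safety objective and no safety variable among its seven dependent variables.
- **Length of recall.** Thirty-two days is the extreme, not the typical interval, as the table shows.

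What these points do not remove is the absence of any described elicitation on Days 3-29, or the disagreement between the text and the schedule.

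**Conclusion.** The point holds in a limited form. The text and the schedule disagree on which visits carry an adverse event review and must be reconciled. On either reading, 27 of the 28 wear days have no scheduled review, and up to 32 days can pass between an event and the next question about it. Mild, transient skin reactions are therefore liable to be under-reported or poorly dated. The documents give no basis for putting a number on the undercount, and they do not show that events will in fact be missed. This is a worthwhile and inexpensive improvement to safety capture; it does not invalidate the trial.

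The day counts rest on two assumptions. The first is that pellets are first applied on Day 2, as the schedule has it. Device Dispensing and Disposition speaks of supply at the initial visit; if application began on Day 1, the maximum would be 34 − 1 = 33 days. The second is that the return window means study Days 30-34, as in the schedule, although one sentence in Study Design and Procedures could be read as counting from the end of treatment.

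**What to change.** 1. Reconcile Safety Assessments with the Schedule of Time and Events, so that both name the same visits for adverse event review.
2. Unless the Patient Diary Sheet already has it, add one entry per day, completed at the placement check that is already required: skin reaction or other new problem, yes or no; what; and site. Site is the useful field because the risk section foresees other positions.
3. Transcribe these entries to the Adverse Event Case Report Form at the reconciled final review visit. This is currently Visit 4, where the schedule also has unused pellets logged in.
4. Report visit-elicited events for both groups. Report diary-sourced events separately, as a description of the experimental group.

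The cost is one added entry on an existing form and one transcription step. The drawback is that diary-sourced events exist in one arm only and cannot be compared between arms. Pooling them with visit-elicited events would make ascertainment unequal between the groups, which is why they must be kept apart.

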- Results in a congenital anomaly or birth defect.

Non-serious adverse events are all events that do not meet the criteria for a “serious” adverse event.

Severity: Each adverse event will be assessed for its severity, or the intensity of an event experienced by the subject using the following:

- Mild: Discomfort noticed, but no disruption to daily activity.
- Moderate: Discomfort sufficient to reduce or affect normal daily activity.
- Severe: Inability to work or perform normal daily activity.

Deaths: The investigator will notify the Sponsor as soon as possible, preferably within 24 hours but in no event later than 48 hours, of learning of a subject’s death, regardless of whether the death is related or unrelated to the investigational drug. The investigator will attempt to determine, as conclusively as possible, whether the death is related to the device. The cause of death and the investigator’s discussion regarding whether or not the death was device-related will be described in a written report.

Pre-existing Conditions: Pre-existing conditions will not be reported as an adverse event unless there has been a substantial increase in the severity or frequency of the problem which has not been attributed to natural history.

Unanticipated Adverse Device Effects: An unanticipated adverse device effect is defined as any serious adverse effect on health or safety, or any life-threatening problem, or death caused by, or associated with, a device; if that effect, problem, or death was not previously identified in nature, severity, or degree of incidence in the investigational plan, or application (including supplementary application), or any other unanticipated serious problem associated with a device that relates to the rights, safety, or welfare of subjects.

If an unanticipated adverse effect occurs, the investigator will promptly notify the sponsor of such an event within 24 hours of first learning of the event. The investigator will notify the IRB of such an event as soon as possible, but no later than ten (10) working days after first learning of the event.

Statistical Plan

TITLE: The Effects of *ProFoveate*™ on Reducing Self- Stimulating Behaviors In Children Diagnosed With Autism Spectrum Disorders.
PI: [name]
Co-I: [name]

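### The causality level Possibly Related is defined as likely or very likely, so an adverse event that is plausible but not likely has no clear category

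*Protocol*

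**What the plan says.** Protocol, Safety Assessments, paragraph on the relationship of adverse events to the device. The study physician makes the judgement, and the list is closed: "The relationship will be assessed using the following categories". Four levels follow.

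- *Definitely Related*: "A direct cause and effect relationship between the investigational device and the adverse event exists".
- *Possibly Related*: a direct causal link that "has not been clearly demonstrated, but is likely or very likely".
- *Unlikely Related*: a direct causal link between "the investigational device and the adverse event is improbable, but not impossible".
- *Unrelated*: "The adverse event is definitely not associated with the investigational device".

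There is no *Probably Related* level. Nothing else in the protocol redefines possible or says how to grade an event that lies between likely and improbable.

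Two other statements in the same section bear on the consequence. Recording does not depend on causality: "All adverse events occurring during the course of the study will be recorded on the Adverse Event Case Report Form". The definition of an unanticipated adverse device effect has its own test of connection, which includes "death caused by, or associated with, a device".

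**The concern.** A label and its definition should point the same way. Here the label invites the physician to choose the level whenever the device could have been the cause, while the definition admits only events where the device probably was. The two instructions agree for strong cases and disagree for the ordinary doubtful case, which is where a causality scale has to work.

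Doubtful cases are realistic in this trial. The patch sits behind the right ear after cleaning with alcohol (Study Treatment Instructions). The recording electrodes include one on each mastoid, applied after alcohol and skin preparation cream and held with tape (Study Design and Procedures). Ear pulling and scratching are among the listed self-stimulating behaviours. Abrasion and latex in the adhesive are named as device risks, and the section on recording risks mentions one earlier small rash from the electrode tape. Redness near the ear could have more than one explanation, and a physician might honestly say that the device is a plausible cause but not a likely one.

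The protocol says that use of this product in autism is unexplored. How local events are attributed to it is therefore a useful part of what the pilot can report, and it should not turn on whether the physician read the label or the definition.

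**Working it through.** No arithmetic applies, and the protocol gives no figure to reproduce. The check sets the four definitions side by side, looks for a gap, and then asks what depends on them.

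**Step 1. Label against definition.**

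| Label | Strength of link in the definition | Do they agree? |
|---|---|---|
| Definitely Related | established | yes |
| Possibly Related | not demonstrated, but likely or more | no: this is the meaning of probably |
| Unlikely Related | improbable, short of impossible | yes |
| Unrelated | excluded | yes |

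Only the second level disagrees with itself.

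**Step 2. Place a plausible but not likely event.** Take an event for which the device is a reasonable candidate but no better supported than another cause.

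- *Definitely Related* fails, because no causal link is established.
- *Possibly Related* fails by definition, because the link is not likely. It fits by label.
- *Unlikely Related* fits only if everything short of likely counts as improbable. If improbable keeps its ordinary sense, it fails.
- *Unrelated* fails, because the device has not been ruled out.

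**Step 3. The possible outcomes.**

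| How the physician reads the scale | Code given |
|---|---|
| Definition, with improbable meaning anything less than likely | Unlikely Related |
| Definition, with improbable in its ordinary sense | no level fits; the nearest level left is Unlikely Related |
| Label | Possibly Related |

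The same event can receive two different codes from a physician acting in good faith. Following the definition moves it down one level from what the label suggests.

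**Step 4. What depends on the code.**

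- Recording: nothing. All adverse events are recorded, and the definition of an adverse event applies whether or not the investigator thinks the device was involved.
- Notice of deaths: nothing. It is required whether the death is related or not.
- Notice of unanticipated device effects to the sponsor and the IRB: no direct dependence. That definition uses its own words and does not name the four levels. A physician who has already coded an event *Unlikely Related* may be less ready to call it associated with the device, but the protocol does not state that connection.
- Efficacy analysis: nothing. None of the seven dependent variables in the Statistical Plan is a safety measure.
- Description of device relationship in the results: this depends on the code directly.

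**The case against.** The strongest reply is that the scale can be read as complete. If likely and improbable are taken as opposites, the four levels cover every case and nothing falls between them. That is a permissible reading, so a strict gap is not certain. It does not remove the problem, because on that reading the plausible event is coded *Unlikely Related* while the label still points to *Possibly Related*.

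A second reply is that a four-level scale is a legitimate choice and the protocol need not have five. This stands. The defect is the mismatch within one level, and it can be cured without adding another.

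A third is that the doubtful case may be uncommon. Recordings take place only at Visits 2 and 4, whereas the patch is worn on days 2 to 29. The protocol reports only one tape rash in 6 years of the lab, and an abrasion directly under a pellet would usually be judged likely and so already meets the second definition. This also stands: the documents show that doubtful events can occur, not that they will be frequent.

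Three stronger readings are tempting, and the documents support none of them.

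- A reader might infer that the scale biases attribution towards not related. The direction is not fixed, because a physician who follows the label does not grade down. Even when an event is graded down, it goes to *Unlikely Related*, which the protocol nowhere merges with *Unrelated*.
- A reader might divide by the 15 children in the experimental group and say that one or two recoded children move a device-related rate by 1/15 = 6.7 or 2/15 = 13.3 percentage points. The protocol defines no such rate and does not say which levels would count. Those figures are only the weight of one or two children in any count out of 15, and they say nothing about how often the wording would misplace an event.
- A reader might fear that events go unreported. Step 4 of the check shows that no recording or notification rule is tied to these levels.

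**Conclusion.** The point holds in a limited form. The label *Possibly Related* contradicts its own definition, and the level below it is worded as improbable. An event that is plausible but not likely therefore has no clear category and may be coded either *Possibly Related* or *Unlikely Related*. Causality coding can be inconsistent and can be graded down by one level.

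The harm is confined to how relationship to the device is coded and tabulated, with a possible but unstated influence on judging whether a serious event is associated with the device. No adverse event drops out of the record, and no endpoint is touched. The number of events affected cannot be estimated from the protocol.

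The conclusion assumes that the adverse event form, which is not shown, carries the same four levels and definitions, and that no separate instruction to the study physician resolves the mismatch. It does not depend on whether improbable is read narrowly or broadly, since both readings leave label and definition in conflict. This is a statement that the protocol makes in full, so it is not a detail left for a statistical analysis plan. The correction is worth making before events are coded, mainly because it is cheap and because local skin events are the named device risk in a first use of this kind in children with autism.

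**What to change.** Redefine *Possibly Related* as a relationship that is plausible and cannot be ruled out. Then choose one of two ways to place the stronger links:

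- add a level *Probably Related* for links that are likely or very likely but not demonstrated; or
- keep four levels and word *Possibly Related* so that it covers everything from plausible to very likely.

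Either choice removes the conflict. The first keeps more information, and the second changes less. Make the same change on the adverse event form, so that the physician sees one set of definitions.

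The cost is a few lines of text in the protocol and the form. The count of possibly related events may come out slightly higher, because plausible events would no longer be pushed to *Unlikely Related*. Recording, notification and the efficacy analysis are unaffected.
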